Statistical analysis plan – A controlled trial investigating the effects of mindfulness

Inclusion criteria: All pregnant women who had registered at one of the 63 antenatal clinics in Stockholm County between 2016-11-01 and 2018-01-31 were eligible for the study.

Exclusion criteria: Multiple pregnancies.

Causal factors: The 63 antenatal clinics were randomized to two groups, one designated as the Mindfulness group, the other as the Standard-care group. Midwives at the clinics in the Mindfulness group employed the Mindfulness method; midwives at the Standard-care clinics continued to employ established methods.

All the women registered at an antenatal clinic practicing standard care belong to the Standard-care group, and all women registered at a clinic practicing Mindfulness belong to the Mindfulness group.

Observation time, primary outcome measures: The women are monitored from gestational week 32+0 onward until the delivery. The primary outcome measure is determined by the baby's Apgar score measured five minutes after birth. The adverse outcome category is defined as an Apgar score under seven. A stillbirth is scored as 0 and thereby included in the adverse outcome category.

Observation time, secondary measures: The women are monitored from gestational week 32+0 onward until the delivery, the secondary outcome measure is determined by the number of times the woman seeks help at an obstetric clinic because of concern with decreased or altered fetal movement

Observation time, tertiary outcome measures: The woman is monitored from gestational week 32+0 onward until the delivery. The tertiary outcome measure is determined by the baby's Apgar score measured five minutes after delivery. The adverse outcome category is defined by an Apgar score less than four. Stillbirth is recorded as Apgar 0 and thereby included in the adverse outcome category. Another tertiary outcome measure is determined by the baby's death at birth or within seven or respectively 27 days after delivery. Tertiary outcome measures include as well small for gestational age (SGA) and being transferred to the neonatal ward after delivery.

Possible maternal confounding factors: Country of birth, age, body mass index (BMI), previous or current illness educational level, employment, tobacco use, parity, previous intrauterine fetal death, assisted fertilization.

Possible child-related factors: Lethal malformation, lethal illness, genetically related illness.

Possible mediating confounding factors: C section, induced delivery.

Analysis procedure: The analyses will follow the *intention-to-treat* principle. Complete-case analyses will be done alongside with analyses on imputed data sets. Imputation will be

carried out when the possibility of confounding is analyzed. The method that we will use is “multiple imputation by chained equations method (MICE)”. A total of 50 imputed data sets with imputed values for missing information of the possible confounding factors will be calculated. The basis of the imputation will be possible confounding factors in which information is at hand. A prevalence ratio (percentage ratio, ratio with the percentage of the adverse outcome category in the Mindfetalness group and Standard-care group, respectively) will be used as the metric of association. Log-binomial regression will be used to model the prevalence ratio when adjusting for possible confounding factors. Log-binomial regression will also provide 95 percent confidence intervals. If a log-binomial model does not converge a modified regression model according to Zou will be employed. Logistical regression, modelling odds ratio, will be considered if the model regression model according to Zou does not converge.

Possible mediating factors: Mediating factors will be studied in two ways: partly by dividing into subgroups and partly by introducing a variable that represents a possible mediating factor into a statistical model. When a possible mediating factor is introduced into the model, the change in the modeled adjusted prevalence ratio will be interpreted as a metric of the relative effect of the mediating factor.

More information: More information can be found in two published articles, see below, as well as in <https://clinicaltrials.gov/ct2/show/NCT02865759?term=[name]&rank=1>.

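### Does the intention-to-treat analysis take in pregnancies that ended before 32+0, or group women by practice instead of by randomised clinic?

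*SAP*

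**What the plan says.** Four parts of the SAP bear on this.

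- **Inclusion and exclusion criteria.** Eligible are "All pregnant women who had registered at one of the 63 antenatal clinics in Stockholm County" between two dates. The only exclusion is multiple pregnancy ("Exclusion criteria: Multiple pregnancies"). There is no entry criterion on gestational age.
- **Causal factors.** "The 63 antenatal clinics were randomized to two groups". Then: "Midwives at the clinics in the Mindfulness group employed the Mindfulness method", while midwives at the other clinics carried on as before. Membership of the intervention group is worded as "all women registered at a clinic practicing Mindfulness belong to the Mindfulness group", with a matching clause for standard care.
- **Observation time** (primary, secondary and tertiary outcome measures). "The women are monitored from gestational week 32+0 onward until the delivery". The tertiary paragraph says the same in the singular. Stillbirth is scored as Apgar 0 inside the primary and tertiary paragraphs.
- **Analysis procedure.** "The analyses will follow the *intention-to-treat* principle". Complete-case analyses run alongside analyses of multiply imputed data. Imputation is for missing confounders only. The effect measure is the ratio of the percentages in the adverse category, and the denominator is not defined further.

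**The concern.** Two things look out of line.

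The first is the denominator. A woman who registers and then miscarries, or delivers at 28 weeks, is eligible and has a group, but is never under observation as the outcome sections define it. No sentence says what becomes of her. If her baby's Apgar score were counted, the primary outcome would include events that arose before the observed period. Low Apgar scores can be expected to be commoner in very early births, so a real effect would be pulled towards 1.

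The second is the grouping. Intention-to-treat at clinic level means analysis by the arm to which the clinic was randomised. A sentence that assigns women by what the clinic practises could be read as an as-treated rule. If some clinics did not take up the method, moving them to the control group would give up the protection of randomisation. Read literally, a woman registered at two clinics of different arms would also belong to both groups.

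**Working it through.** The SAP states no event rate, sample size or early-delivery rate, so there is no figure of its own to reproduce. All rates below are assumptions.

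**1. What the text allows for pregnancies that ended before 32+0.** There are three possible treatments.

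*(a) Left out.* The outcome is an Apgar score observed from 32+0 onward. A pregnancy that ended earlier has no outcome in that window. Imputation covers confounders and not outcomes, so such a woman drops out of both the complete-case and the imputed analyses. The ratio is that of pregnancies ongoing at 32+0.

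*(b) Kept as non-events.* Let f1 and f0 be the shares of early endings in the intervention and standard-care arms. Then

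observed ratio = true ratio × (1 − f1)/(1 − f0).

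- f1 = f0: the factor is 1 and the ratio does not move. Only the percentages fall, by the factor 1 − f (1% becomes 0.995% at f = 0.5% and 0.90% at f = 10%).
- f1 = 2%, f0 = 3%: 0.98/0.97 = 1.010, so 0.75 becomes 0.758.
- f1 = 5%, f0 = 10%: 0.95/0.90 = 1.056, so 0.75 becomes 0.792. This needs one arm to lose twice the share of the other.

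*(c) Early outcomes counted as events.* With f the share of births before 32+0 (equal in both arms), r the share of those that are adverse, 1.1% adverse later and a true ratio of 0.75,

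observed ratio = [f·r + (1 − f)·0.011·0.75] / [f·r + (1 − f)·0.011].

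| f | r | f·r | (1 − f)·0.011 | Early share of control-arm events | Observed ratio |
|---|---|---|---|---|---|
| 0.006 | 0.15 | 0.00090 | 0.010934 | 7.6% | 0.769 |
| 0.010 | 0.25 | 0.00250 | 0.010890 | 18.7% | 0.797 |
| 0.015 | 0.35 | 0.00525 | 0.010835 | 32.6% | 0.832 |

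A wider grid (true ratio 0.80, control prevalence 0.5% to 2%, f from 0.5% to 10%, r from 10% to 100%) gives ratios from 0.805 to 0.991. So (c) could matter a good deal, but it is the treatment that the stated window rules out. The stillbirth rule does not bring it back. That rule has no gestational limit of its own, but it stands within paragraphs that open with the 32+0 window.

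**2. Grouping by practice.** Set in order, the sentences under Causal factors say that clinics were randomised to two groups, that clinics in the Mindfulness group used the method and the others did not, and that women at a clinic practising a method belong to the group of that name. The second step makes practice and allocation the same thing, so the third is shorthand for the randomised arm. The intention-to-treat sentence governs should a clinic depart from its allocation, and the SAP reports none.

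For scale only: assume 31 intervention and 32 control clinics of equal size (the SAP gives only the total of 63), 3 intervention clinics that did not adopt the method, 1.5 times the baseline risk in those three, and no effect. Grouping by practice then gives 1/[(32 + 3 × 1.5)/35] = 35/36.5 = 0.959. Each of those inputs other than the total is invented.

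**The case for a change.** The best case for a change is that the denominator of the primary analysis is core SAP content, that the SAP sets out eligibility itself, and that the window is labelled observation time and not an entry criterion. Two programmers could build different data sets, and a choice made after the data are seen is a freedom that a plan should remove. One clarifying sentence would cost almost nothing.

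Part of this stands. The restriction to pregnancies ongoing at 32+0 is implied and not written, and a reference to randomised allocation would be tidier than one to practice. But the two data sets that the text can support, (a) and (b), give the same ratio when early endings are equally frequent in the arms, and nearly the same under a modest imbalance. The data set that would give a materially different answer requires the programmer to disregard a window stated for every set of outcomes. The case of a woman registered in both arms is hypothetical on this text, and a rule for change of clinic may well stand in the protocol, which is not at hand.

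**Conclusion.** No change follows. Followed as written, the SAP counts outcomes from 32+0 to delivery, and its intention-to-treat principle ties each woman to the randomised arm of her clinic. Early endings either drop out or sit in the denominator as non-events. In the second case the ratio is unmoved if they are equally frequent in both arms, and goes from 0.75 to 0.758 with 2% against 3%. The dilution to between 0.77 and 0.83 rests on assumed rates and on counting events outside the window. The 0.96 for grouping by practice rests on an assumed failure of three clinics that the SAP does not report. The remainder is missing detail and one loosely chosen word, which an analyst would resolve sensibly from the plan's own window and principle. The conclusion would be different only if outcomes before 32+0 were in fact counted, or if a clinic that departed from its allocation were analysed by its practice. The SAP provides for neither.

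### The secondary outcome is a count of visits per woman, but the only planned analysis is a prevalence ratio for a category that is never defined for visits

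*SAP*

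**What the plan says.** Observation time, secondary measures: "the secondary outcome measure is determined by the number of times the woman seeks help at an obstetric clinic" because of concern about fetal movement, with follow-up from week 32+0 until delivery. No threshold or category follows.

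The Apgar outcomes are handled differently. For the primary outcome, "The adverse outcome category is defined as an Apgar score under seven". For the tertiary Apgar outcome, "The adverse outcome category is defined by an Apgar score less than four". The remaining tertiary outcomes (death, small for gestational age, transfer to the neonatal ward) are yes/no by nature.

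Analysis procedure names one metric of association, a prevalence ratio, described as the "ratio with the percentage of the adverse outcome category in the Mindfetalness group and Standard-care group". On the model it says: "Log-binomial regression will be used to model the prevalence ratio when adjusting for possible confounding factors". Two fallbacks follow, each triggered by non-convergence: "If a log-binomial model does not converge a modified regression model according to Zou will be employed", and "Logistical regression, modelling odds ratio, will be considered if the model regression model according to Zou does not converge". The section names no count model, ratio of means or rate ratio.

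**The concern.** A percentage in a category cannot be computed from a count until someone says which counts fall in the category. Visits are the only outcome in the SAP that is neither binary by nature nor given a cut-off, so the stated analysis does not estimate the declared outcome.

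Two things are at stake. First, the usual way out, any visit versus none, answers whether more women sought help. The declared outcome asks how many times they sought help. An intervention that makes women attend repeatedly could look smaller than it is. Second, because no cut-off is fixed, it could be chosen after the data are seen, and the estimate depends on it. For a method that asks women to attend to fetal movements, the added volume of visits is a main measure of its burden on obstetric care.

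**Working it through.** **Text check.** Each outcome set against the single planned metric:

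| Outcome | Form as declared | Category given? |
|---|---|---|
| Primary: Apgar at 5 minutes | score | yes, under 7 |
| Secondary: visits for fetal movement | count per woman | no |
| Tertiary: Apgar at 5 minutes | score | yes, under 4 |
| Tertiary: death, small for gestational age, neonatal transfer | yes/no | not needed |

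Only visits fail to fit the metric. The Zou model does not fill the gap. It enters only when the log-binomial model fails to converge, as another way to estimate the same prevalence ratio.

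**Size.** The SAP gives no visit rate or dispersion, so there is no figure to reproduce and every input here is an assumption: standard-care mean m = 0.10 or 0.20 visits per woman; Mindfulness mean 1.3m (ratio of means 1.30); counts Poisson or negative binomial with k = 0.5 or 0.25, the same in both arms.

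Formulas:
- Poisson: P(0) = exp(−m). Negative binomial: P(0) = (k/(k+m))^k.
- P(any) = 1 − P(0).
- Share of visits that are repeats = (m − P(any))/m.
- Share of extra visits not counted = 1 − [P(any; 1.3m) − P(any; m)]/(0.3m).

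Mildest case, Poisson with m = 0.10:
- P(any) = 1 − exp(−0.10) = 9.52% against 1 − exp(−0.13) = 12.19%; ratio 1.28.
- Repeat share in standard care = (0.1000 − 0.0952)/0.1000 = 4.8%.
- Per 100 women there are 3.00 extra visits but 2.67 extra women with a visit; 1 − 2.67/3.00 = 11% not counted.

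Most dispersed case, k = 0.25 with m = 0.20:
- P(any) = 1 − (0.25/0.45)^0.25 = 13.67% against 1 − (0.25/0.51)^0.25 = 16.33%; ratio 1.19.
- Repeat share in standard care = (0.2000 − 0.1367)/0.2000 = 31.7%.
- Per 100 women there are 6.00 extra visits but 2.66 extra women; 1 − 2.66/6.00 = 56% not counted.

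Intermediate case, k = 0.5 with m = 0.10: 8.71% against 10.91%; ratio 1.25; repeat share 12.9%; 27% not counted.

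**Dependence on the cut-off.** Under the same assumptions, with P(1) = m·exp(−m) for Poisson and P(1) = k·(m/(k+m))·P(0) for the negative binomial, and so on for higher counts:

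| Category | Prevalence ratio (ratio of means 1.30) |
|---|---|
| at least 1 visit | 1.19 to 1.28 |
| at least 2 visits | 1.39 to 1.66 |
| at least 3 visits | 1.61 to 2.15 |

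The lowest cut-off understates the ratio of means and the higher ones overstate it.

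**The case against.** The strongest reply is that the outcome sentence names only the source variable. The primary outcome is worded the same way, as determined by a score, and becomes a category in the next sentence. With one metric planned throughout, the equivalent sentence for visits may simply have been left out, and any visit versus none may have been meant. This is plausible and may be what the authors intended. It does not rescue the text: the SAP says number of times, never says at least one, and on this reading the outcome wording itself needs correcting.

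The illustration also has limits. Its inputs are assumed, and the 56% and 32% come from the most dispersed corner. That the direction is kept under any versus none follows from giving both arms the same k, so it says nothing about a change in dispersion. These points stand, and they limit how far the size can be pressed.

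Two further objections carry less weight. A category might be stated in the protocol or in the sources the SAP refers to, but this SAP fixes both the outcome and the metric, and the two do not match. A count model might seem to need an offset for varying follow-up, but visits per woman from 32+0 to delivery is the declared quantity, so a ratio of mean visits needs none.

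Clustering by clinic would matter for other outcomes too and is not the source of this mismatch. It appears in the remedy because the interval for any new model must respect the unit of randomisation.

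**Conclusion.** The concern holds. The mismatch is certain from the text: a count is declared, the only metric requires a category, and none is given. Its size is conditional on the assumed visit means, ratio of means and dispersion above. If any versus none is used, a ratio of means of 1.30 is reported as 1.19 to 1.28, a modest attenuation with the direction kept in these scenarios. The estimate leaves out 5% to 32% of standard-care visits and 11% to 56% of the extra visits. The consequence is confined to this one secondary outcome. It should be corrected, but it does not threaten the trial's main conclusion.

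**What to change.** Analyse the number of visits per woman from 32+0 to delivery with a log-link count model, either negative binomial or Poisson with robust variance. Report the ratio of mean visits with its 95% confidence interval. Cluster the standard errors by clinic, since under Causal factors "The 63 antenatal clinics were randomized to two groups". Beside it, report the prevalence ratio for at least one visit versus none under the existing plan.

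If a dichotomy was intended all along, reword the outcome as at least one visit versus none and keep the prevalence ratio, with clinic-clustered standard errors.

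The first route costs one extra model on data already collected and a second effect measure in the report. The second costs one reworded sentence and the clustered standard errors.

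### The imputation model for missing confounders names neither the outcome nor the allocated group, so adjustment on imputed data only partly removes chance imbalance

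*SAP*

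**What the plan says.** All the relevant text is under Analysis procedure in the SAP. Missing confounder values are to be filled in by chained equations: "A total of 50 imputed data sets with imputed values for missing information of the possible confounding factors will be calculated". The predictors are then defined: "The basis of the imputation will be possible confounding factors in which information is at hand".

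The maternal factors listed run from country of birth, age and BMI through to assisted fertilization. A short child-related list follows, and then caesarean section and induction as mediating factors. Neither the outcome nor the allocated group is on any of these lists, and no other sentence brings them into the imputation.

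The analysis model is "Log-binomial regression will be used to model the prevalence ratio when adjusting for possible confounding factors", with the group contrast as its target. The SAP also states that "Complete-case analyses will be done alongside with analyses on imputed data sets". Under Causal factors, the unit of allocation is the clinic: "The 63 antenatal clinics were randomized to two groups".

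**The concern.** The imputation model is narrower than the analysis model it serves. The analysis relates outcome to group and confounders. The imputation, as written, uses confounders alone. An imputed value is therefore unrelated to outcome and group, except through the other covariates. Two things follow when a confounder is partly imputed:

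- its association with the outcome is pulled towards the null;
- its difference between the two groups is pulled towards zero.

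Both reduce the amount of imbalance that the adjusted model can remove. The SAP reserves imputation for the step in which confounding is examined, so the specification weakens the imputed analysis at the one task it has. With 63 clinics randomised, chance differences in maternal factors between the groups are possible.

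This is not a systematic bias in favour of either group. Randomisation makes either direction of imbalance equally likely, and mirrored imbalances give equal and opposite errors on the log scale.

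**Working it through.** The SAP gives no missingness rate, outcome rate or confounder prevalence, so there is no figure of its own to reproduce. The check is of mechanism, with assumed inputs.

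**Inputs from the SAP.** Binary primary outcome; log-binomial model; confounders-only imputation; two groups.

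**Assumed inputs.** One binary confounder X with prevalence ratio 2.0 for the outcome; baseline risk 1%; equal group sizes; true group ratio 1.0; a fraction m of X missing completely at random; X not predicted by the other covariates; clustering ignored.

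**Step 1: approximation.** Imputing a fraction m of X without outcome and group shrinks both associations of X by a factor of about (1 − m). The share of the imbalance effect left after adjustment is therefore about 1 − (1 − m)²:

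- m = 0.05: 1 − 0.95² = 0.098
- m = 0.10: 1 − 0.90² = 0.190
- m = 0.20: 1 − 0.80² = 0.360

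**Step 2: exact expected cells.** The expected proportions for group × X × outcome were written down, a fraction m of X was redrawn from its marginal distribution, and the main-effects log-binomial model was fitted by maximum likelihood. The crude ratio is (1 + p₁)/(1 + p₀), with p₀ and p₁ the prevalence of X in the Standard-care and Mindfulness groups. For 18% v 22% it is 1.22/1.18 = 1.034.

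| Prevalence of X, Standard-care v Mindfulness | Crude ratio | Adjusted, 5% missing | 10% missing | 20% missing |
|---|---|---|---|---|
| 20% v 20% | 1.000 | 1.0000 | 1.0000 | 1.0000 |
| 18% v 22% | 1.034 | 1.0033 | 1.0064 | 1.0121 |
| 22% v 18% | 0.967 | 0.9967 | 0.9937 | 0.9880 |
| 20% v 30% | 1.083 | 1.0080 | 1.0156 | 1.0296 |

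On the log scale, 18% v 22% with 10% missing leaves ln(1.0064)/ln(1.0339) = 0.0064/0.0333, or 19%, as in Step 1. At 18% v 22% the ratio for X itself falls from 2.00 to 1.940, 1.882 and 1.768.

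**Step 3: which variables are needed.** For 20% v 30% with 20% missing:

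| Imputation of X uses | Adjusted group ratio |
|---|---|
| neither outcome nor group | 1.0296 |
| group only | 1.0162 |
| outcome only | 1.0163 |
| both | 1.0000 (ratio for X: 2.000) |

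Either variable alone roughly halves the error. Both are needed to remove it.

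**Step 4: second method.** A simulation with 8 million women per scenario used a Poisson (Zou-type) model and confounder ratios of 2 or 3. The share remaining was about 10%, 19% and 35–37% at 5%, 10% and 20% missing with confounders only. With outcome and group added it was between −0.9% and +0.4% across all scenarios, including 30% missing. Letting a second covariate predict X moderately barely changed this.

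**The case against.** **The omission is inferred.** The SAP does not say that only confounders will be used, nor does it exclude outcome or group. That is true. But the sentence defines the basis of the imputation, and a programmer following it would enter confounders only. If the sponsor intends otherwise, the sentence still needs changing.

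**The plan already contains unaffected estimates.** The unadjusted ratio uses no imputed confounder. Under the missing-completely-at-random assumption used above, the complete-case adjusted ratio is also unbiased, with some loss of precision. This stands and limits the harm. It does not mend the imputed analysis: outside that assumption, a gap between the two adjusted results could come from selection of complete cases or from the imputation model, and a reader could not tell which.

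**The effect is small where it is plausible.** This stands too. Suppose 63 equal-sized clinics with a between-clinic standard deviation of 10, 15 or 20 percentage points in the confounder (assumed). The standard error of the group difference is then about 2.5, 3.8 or 5.0 points, so a 10-point imbalance lies about 4, 2.6 or 2 standard errors out. The 18% v 22% rows are the more realistic guide.

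**Several outcomes could multiply the imputations.** A separate imputation for each outcome would exceed the planned 50 data sets. One joint chained-equations model holding group, outcomes, confounders and mediators avoids this.

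**Conclusion.** The concern holds. The SAP states an imputation rule, and followed as written that rule omits two variables of the model it feeds. Confounder–outcome ratios are attenuated, and the imputed-data adjustment leaves about 10%, 19% and 36% of any imbalance effect in place at 5%, 10% and 20% missing.

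In absolute terms the group ratio moves by less than 1% at 18% v 22% with 5–10% missing, and by about 3% at 20% v 30% with 20% missing. These figures rest on the assumed confounder strength, prevalence and missingness, none of which the SAP gives. This is a correction that should be made; it does not threaten the unadjusted result.

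**What to change.** Replace the sentence that defines the imputation basis with:

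> *The imputation model for each analysis will include every variable of that analysis model: the outcome analysed, the allocated group and all possible confounding factors.*

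Where a mediator enters the analysis model, the phrase *every variable of that analysis model* already covers it; naming it in the list would make this plain. To keep to the planned 50 data sets, use one joint chained-equations model containing the group, the outcomes, the confounders and the mediators.

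The cost is one SAP sentence and a few more predictors in the imputation code: two for any single adjusted analysis, more in the joint model. No extra data are needed.

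### Clinics are randomised, but none of the SAP's models allows for clinic, so the 95% intervals are too narrow if outcomes correlate within clinic

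*SAP*

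**What the plan says.** Under Causal factors: "The 63 antenatal clinics were randomized to two groups". Group membership follows the clinic: "All the women registered at an antenatal clinic practicing standard care belong to the Standard-care group", and likewise "all women registered at a clinic practicing Mindfulness belong to the Mindfulness group". Treatment therefore never varies within a clinic, and this is a cluster-randomised design with 63 clusters.

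The primary outcome is binary and recorded per baby at five minutes: "The adverse outcome category is defined as an Apgar score under seven".

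Under Analysis procedure, the effect measure is a prevalence ratio, adjusted by log-binomial regression, and "Log-binomial regression will also provide 95 percent confidence intervals". The first fallback is conditional: "If a log-binomial model does not converge a modified regression model according to Zou will be employed". Logistic regression is considered if that fails too. Missing confounder values are imputed by chained equations in 50 data sets, and "The basis of the imputation will be possible confounding factors in which information is at hand".

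The text has no clinic random effect, GEE, clinic-clustered variance, clinic-level analysis, ICC or design effect.

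**The concern.** The likelihood-based intervals of log-binomial and logistic regression assume that women are independent given the covariates. Women at one clinic share midwives, local routines and catchment area, so their outcomes may be correlated. In this design any such correlation adds directly to the variance of the group comparison, because each clinic contributes to one arm only.

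Zou's method uses a sandwich variance, which could be clustered on clinic. The SAP does not say that it will be, and it reaches that model only on non-convergence. A sandwich variance computed woman by woman does not correct for within-clinic correlation.

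At stake are the prevalence ratio for Apgar below 7 and every other interval from these models. The error runs one way: precision is overstated, and chance variation between clinics could be read as an effect of the method.

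**Working it through.** The SAP gives no sample size, clinic size, event rate or ICC, so it has no figure to reproduce. The check asks how far a nominal 95% interval falls short when clinic is ignored.

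**From the SAP:** 63 clinics, two groups, a binary primary outcome, a prevalence ratio and 95% intervals.

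**Assumed:** 31 v 32 clinics; mean clinic size m of 100, 300 or 500; coefficient of variation (CV) of clinic size 0.5; event rate 1.2%; ICC 0 to 0.001.

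**Formulas**
- Design effect: DE = 1 + ((1 + CV²) × m − 1) × ICC
- Factor by which the interval should be wider: √DE
- Approximate true coverage: 2Φ(1.96/√DE) − 1

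**Worked example**, m = 300 and ICC = 0.0005: DE = 1 + (1.25 × 300 − 1) × 0.0005 = 1 + 374 × 0.0005 = 1.187. √DE = 1.089. Coverage = 2Φ(1.799) − 1 = 92.8%.

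**Simulation:** beta-binomial outcomes, no true effect, 20,000 replicates per setting. The interval is the unadjusted log prevalence ratio interval that ignores clinic.

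| Women per clinic | ICC | DE | √DE | Coverage, formula | Coverage, simulated |
|---|---|---|---|---|---|
| 300 and 500 | 0 | 1.000 | 1.00 | 95.0% | 95.1% |
| 100 | 0.0005 | 1.062 | 1.03 | 94.3% | 94.6% |
| 300 | 0.0001 | 1.037 | 1.02 | 94.6% | 94.8% |
| 500 | 0.0001 | 1.062 | 1.03 | 94.3% | 94.3% |
| 300 | 0.0005 | 1.187 | 1.09 | 92.8% | 92.7% |
| 500 | 0.0005 | 1.312 | 1.15 | 91.3% | 91.5% |
| 300 | 0.001 | 1.374 | 1.17 | 90.5% | 90.8% |
| 500 | 0.001 | 1.624 | 1.27 | 87.6% | 87.6% |

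The false-positive rate is 100% minus coverage. At ICC 0.001 it is 9.2% (m = 300) to 12.4% (m = 500) instead of 5%.

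**Sensitivity to the event rate.** At ICC 0.0005 the false-positive rate for m = 300 and m = 500 is 6.9% and 8.4% at an event rate of 0.8%, and 7.0% and 8.7% at 2%. The assumed rate matters little.

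**What such an ICC means.** At a mean of 1.2%, ICC 0.0005 gives a between-clinic standard deviation of √(0.0005 × 0.012 × 0.988) = 0.0024. Under a beta distribution, the 5th to 95th percentile of true clinic rates is 0.83% to 1.63%.

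**Larger ICCs.** With equal clinics, where DE = 1 + (m − 1) × ICC, coverage by formula at m = 300 is 78.5% for ICC 0.005 and 67.4% for ICC 0.01. At m = 600 and ICC 0.01 it is 54.2%. A second simulation, at an assumed 1.1% event rate, gave 78.9%, 68.4% and 54.5%.

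**Does the remedy work?** With clinic-robust standard errors and a t distribution on 63 − 2 = 61 degrees of freedom, simulated coverage in the 300 to 500 settings was 94.6% to 95.0%.

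**The case against.** The strongest counter-argument is that the harm may be trivial. Low Apgar is rare. It is recorded at delivery, whereas the randomised units are antenatal clinics. The planned model adjusts for country of birth, BMI, education, parity and other factors that may explain part of the variation between clinics, while the simulation is unadjusted. With 100 women per clinic, or an ICC of 0.0001, coverage stays within a point of 95%. All of this stands as a caution about size. It does not make the ICC zero, and the SAP gives no basis for assuming that it is.

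Clinic's absence from the confounder lists is not in itself a fault. Group is constant within clinic, so indicators for all clinics would be collinear with group. The absence shows only that clustering is not handled there either. Nor does leaving clinic out of the imputation basis narrow the intervals by itself. What matters here is that the variance within each imputed data set must allow for clinic.

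The public text has parts removed and refers to published articles and a registry record. The Analysis procedure section nevertheless names its models and the source of its intervals, and appears intact.

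**Conclusion.** The concern holds. The SAP's own description of the design makes the clinic the randomised unit, and its stated source of intervals ignores that unit. This is a mismatch within the document and not a detail left to the protocol.

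Confidence is high that the allowance for clinic is absent and that any positive ICC makes the intervals too narrow. The size is unknown. Under the assumptions shown it runs from nothing at ICC 0, through a shortfall of about 2 to 4 percentage points at ICC 0.0005, to about 4 to 7 points at ICC 0.001 (300 to 500 women per clinic), and more at larger ICCs. Because it affects the primary comparison, it must be fixed.

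**What to change.** State under Analysis procedure that all effect estimates and intervals account for clinic as the cluster. This should cover the main model, every fallback and each of the 50 imputed data sets before pooling.

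Name one method in advance. Suitable choices include:
- the planned log-binomial model with clinic-robust standard errors, which is the smallest change;
- modified Poisson GEE with clinic-robust standard errors and a small-sample correction (about 61 degrees of freedom);
- a clinic random effect, or a clinic-level analysis.

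State how the small-sample correction combines with pooling over imputations, since the simulation checked it only in unadjusted, complete data. Do not add clinic as an ordinary fixed covariate. Report the ICC for each outcome.

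The cost is SAP wording and a little more analysis work. No new data are needed, because the clinic where each woman registered already defines her group. Intervals widen if the ICC is above 0 and barely change if it is near 0.
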